5.5. BCX7353 Risk/Benefit Analysis

Given that BCX7353 is a small molecule kallikrein inhibitor with data available from completed Phase 1 single and multiple dose studies, a Phase 2 study in subjects with HAE, and two ongoing randomized, double-blind, placebo-controlled Phase 3 studies, there is an acceptably low risk of severe or serious adverse reactions. Potential risks and findings from nonclinical and clinical studies of BCX7353 are discussed in the Section 6 of the IB (Summary of Data and Guidance for the Investigator).

5.6. Benefits of Trial Participation

Study subjects will receive regular medical care for the duration of the study. Subjects may experience a reduction in the number of attacks while receiving BCX7353. BCX7353 produced a statistically significant and clinically meaningful reduction in the rate of HAE attacks compared to placebo for the primary endpoint in the ITT population of Study BCX7353-302.

The development of BCX7353 may be of benefit to the wider community/patients with HAE.

5.7. Overall Benefit-Risk Assessment

The risks from daily oral administration of BCX7353 seen to date in both preclinical and clinical studies were primarily mild, monitorable, and reversible. Overall, the clinical efficacy and safety data support a favorable benefit risk profile for BCX7353. In the 24-week, adequate, well-controlled pivotal efficacy and safety trial in adolescents and adults with Type I or II HAE, BCX7353 150 mg QD treatment for 24 weeks versus placebo resulted in statistically significant and clinically meaningful reductions in monthly HAE attack rate, monthly rate of HAE attacks requiring acute rescue therapy, the monthly rate of moderate or severe HAE attacks, and the monthly rate of laryngeal HAE attacks. Results of sensitivity and subgroup analyses of the HAE attack rate were consistent with those of the primary efficacy analysis. The safety data from controlled trials and long-term open-label studies is sufficient to assess the safety of BCX7353 in the proposed rare disease HAE population. Important potential risks are delayed-type hypersensitivity reactions (rash) and transaminase elevations. Hypersensitivity rash was identified as a signal early in development; few events were reported, and these were mild to moderate, self-limited, not dose dependent, and resolved with continued dosing without recurrence. Increases in ALT/AST were generally transient, asymptomatic, not dose dependent, and heavily confounded by prior administration of androgens. The overall benefit-risk balance is therefore considered to be acceptable.

6. TRIAL OBJECTIVES

6.1. Objectives

6.1.1. Primary Objective

- To evaluate the long-term safety and tolerability of daily dosing of oral BCX7353 in subjects with HAE

6.1.2. Secondary Objectives

- To assess the effectiveness (ie, HAE attack frequency, severity, and disease activity over time) of BCX7353 during long-term administration
- To evaluate QoL during long-term administration of BCX7353
- To evaluate subject's satisfaction with medication during long-term administration of BCX7353

7. OVERALL STUDY DESIGN AND PLAN

This is a single-arm open-label study designed to evaluate the long-term safety of prophylactic treatment with daily oral BCX7353 in subjects with HAE. The study will also evaluate the long-term effectiveness and impact on QoL or general well-being of subjects who receive BCX7353 prophylactic treatment, and the subject's satisfaction with the medication. Based on the final results from Part 1 of the randomized, double-blind, placebo-controlled efficacy study (BCX7353-302), the dose of BCX7353 used in this study is 150 mg QD.

Subjects may be enrolled once all eligibility criteria and study requirements are met. On-treatment study visits will occur at Weeks 4, 12, 24, 48, 72, and 96. An independent DMC has been reviewing the safety data from this study in concert with the accumulating safety information generated across the BCX7353 clinical development program. The DMC met at a frequency of approximately every 12 weeks until a total of approximately 200 subjects across the Phase 3 Study, BCX7353-302, and the current study (BCX7353-204) completed 48 weeks of dosing with active drug. Since a total of over 200 subjects have completed 48 weeks across the studies, the DMC is now provided with data every 6 months until the last subject completes the study or approval is obtained in the first country globally. A formal meeting of the DMC members will not be required; however, if the data review identifies any concern, the DMC members may elect to hold a formal DMC meeting. In addition, the emergence of a new, clinically significant safety signal may prompt an ad hoc DMC review.

Approximately 475 subjects will be enrolled into the study, with approximately 250 subjects planned to be enrolled in the US. Subjects will be eligible to receive BCX7353 for up to 96 weeks, until the product becomes commercially available, or until the Sponsor discontinues development of the product for the prevention of angioedema attacks, whichever comes first.

A study schema is shown in [Figure 1](#).

[figure not shown]
All subjects will be instructed to complete their diaries to document all angioedema attacks that occur.

Acute attacks of angioedema will be treated in accordance with the subject's normal standard of care. Treatment for acute attacks of HAE will not be provided by the Sponsor.

Subjects will complete the angioedema quality of life questionnaire (AE-QoL) to assess health-related QoL and the Treatment Satisfaction Questionnaire for Medication (TSQM) to assess their satisfaction with the study medication. Additionally, subjects will be assessed if days were lost from school and/or work.

Safety and tolerability will be evaluated through assessments of AEs, laboratory analyses (clinical chemistry, hematology, coagulation and urinalysis), vital signs, ECGs, and physical examinations at the study visits indicated in the schedule of assessments (see [Table 3](#)).

Figure 1. Study Schema

Abbreviations: EOT = end of treatment; WK = week.

7.1. Endpoints

7.1.1. Safety Endpoints

The primary objective of the study is to obtain long-term safety of BCX7353. The safety endpoints will include the following:

- The proportion of subjects who discontinue BCX7353 due to a TEAE
- The proportion of subjects with treatment-emergent SAEs
- The proportion of subjects with TEAEs
- The proportion of subjects with treatment-emergent Grade 3 or 4 AEs
- The proportion of subjects with treatment-emergent, treatment-related AE consistent with a drug rash
- The proportion of subjects with treatment-emergent Grade 3 or 4 laboratory abnormalities

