12. ADVERSE EVENT MANAGEMENT AND REPORTING

12.1. Adverse Events

AEs will be assessed and recorded from the time of signing of the informed consent through the appropriate follow-up period. Full details on recording and reporting AEs are provided in Section [12.1.2](#).

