12.1.1. Definitions

12.1.1.1. Adverse Event

An AE is any untoward medical occurrence in a clinical study subject. No causal relationship with the study drug or with the clinical study itself is implied. An AE may be an unfavorable and unintended sign, symptom, syndrome, or illness that develops or worsens during the clinical study. Clinically relevant abnormal results of diagnostic procedures including abnormal laboratory findings (eg, requiring unscheduled diagnostic procedures or treatment measures, or resulting in withdrawal from the study) are considered to be AEs. If the diagnostic procedure prompts no additional treatment, visits, or monitoring, it will not meet the definition of an adverse event.

This includes the following:

- AEs not previously observed in the subject that emerge during the protocol-specified AE reporting period (see Section [12.1](#)), including medical triggers resulting in an HAE attack. Emotional stress will not be considered an AE unless it results in a medical diagnosis or requires medical treatment.
- Findings from protocol-mandated interventions. This can include laboratory assessments performed in the course of the trial. AEs should only be reported if the abnormalities are changes from baseline and are clinically significant as described above.
- Pre-existing medical conditions (other than the condition being studied) judged by the Investigator to have worsened in severity or frequency or changed in character during the protocol-specified AE reporting period. When recording such events on an AE/SAE eCRF page, it is important to convey the concept that the preexisting condition has changed by including applicable descriptors (eg, “more frequent headaches”).

An adverse reaction is defined in Article 2(n) of Directive 2001/20/EC as follows: all untoward and unintended responses to a study drug/IMP related to any dose administered. The definition covers also medication errors and uses outside what is foreseen in the protocol, including misuse and abuse of the product. The definition implies a reasonable possibility of a causal relationship between the event and the study drug/IMP. This means that there are facts (evidence) or arguments to suggest a causal relationship.

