### **9.3. Adverse Event Preferred Term and Body/Organ System Summary Tables**

The following are safety endpoints:

- Proportion of subjects with TEAEs
- Proportion of subjects with TESAEs
- Proportion of subjects who discontinue BCX7353 due to a TEAE
- Proportion of subjects with treatment-emergent Grade 3 or 4 AEs
- Proportion of subjects with treatment-emergent, treatment-related AE consistent with a drug rash
- Proportion of subjects with treatment-emergent Grade 3 or 4 laboratory abnormalities

AEs will be mapped to a MedDRA version 19.1 SOC and PT. If a subject experiences multiple events that map to a single preferred term, the greatest severity grade according to the Division of Microbiology and Infectious Diseases (DMID) November 2007 criteria and strongest investigator assessment of relation to study medication will be assigned to the preferred term for the appropriate summaries. Should an event have a missing severity or relationship, it will be classified as having the highest severity and/or strongest relationship to study medication. All AEs will be listed for individual subjects showing both verbatim and preferred terms.

TEAEs are defined as AEs that occurred on or after first dose of study treatment through 30 days post-discontinuation of study treatment. All AEs that occurred prior to the initiation of study treatment or those recorded after 30 days after the last dose of study treatment will be excluded from the tables but will be included in the listings.

Drug-related events are defined as those AEs that the Investigator believes were possibly, probably, or definitely related to the study drug.

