## **9.6. Laboratory Data**

The following is a safety endpoint:

- Number and proportion of subjects who experience a treatment-emergent Grade 3 or 4 laboratory abnormality

A listing of clinical laboratory evaluations is provided in protocol Section 11.1.6.

Clinical laboratory assessments and corresponding changes from baseline will be summarized for each laboratory panel by treatment group and visit. Laboratory abnormalities will be graded according to the DMID Adult Toxicity Table (publish date: November 2007; see Protocol Appendix 16.1). Any graded abnormality that occurs following the initiation of study drug and represents at least one-grade increase from the baseline assessment is defined as treatment emergent.

Urinalysis results will be summarized by treatment and visit and listed by subject and treatment.

The number and percentage of subjects experiencing treatment-emergent graded toxicities will be summarized. Treatment-emergent Grade 3 or 4 laboratory abnormalities will be summarized separately. Laboratory toxicity shifts from baseline to worst post-baseline assessments will be summarized.

The number and percentage of subjects having elevations in liver enzyme abnormalities (alanine aminotransferase [ALT], aspartate aminotransferase [AST], or bilirubin) in relation to fold above the upper limit of normal (ULN) will be summarized by treatment group.

The following categories of abnormal hepatic laboratory values will be evaluated for any occurrence among all post baseline assessments (where “and” indicates elevations occurring at the same visit). Within each treatment group and laboratory parameter grouping, a subject may be counted once per elevation criteria using the worst-case result. That is, a subject with a worst-case ALT elevation  $>3 \times$  the ULN for a given treatment group would be counted once in the ALT  $> 1.5 \times$  ULN category and once in the ALT  $> 3 \times$  ULN category, regardless of how many ALT elevations the subject had that met the  $> 3 \times$  ULN and  $> 1.5 \times$  ULN elevation criteria.

- ALT and/or AST > 3 × ULN and total bilirubin > 1.5 or 2 × ULN
- AST > 1.5, 3, 5, 10, and 20 × ULN
- ALT > 1.5, 3, 5, 10, and 20 × ULN
- Total bilirubin > 1, 1.5, or 2 × ULN
- Alkaline phosphatase (ALP) > 1.5 × ULN

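### SAP 9.3 defines a TEAE by date of occurrence alone, so an AE already open at first dose that worsens on BCX7353 is missed by the AE endpoints if it stays under its original record

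*Protocol*

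**What the plan says.** Protocol 7.1.1 lists six safety endpoints, and five of them are proportions of subjects with some kind of treatment-emergent AE. One is "The proportion of subjects with treatment-emergent Grade 3 or 4 AEs". The protocol does not define treatment-emergent for AEs.

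The only definition is in SAP 9.3: "TEAEs are defined as AEs that occurred on or after first dose of study treatment through 30 days post-discontinuation of study treatment". A further sentence names what the tables leave out and only the listings keep. It starts with "All AEs that occurred prior to the initiation of study treatment" and goes on to late records, more than 30 days past the final dose. Worsening is not mentioned.

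AE collection begins well before dosing. Protocol 12.1 states: "AEs will be assessed and recorded from the time of signing of the informed consent through the appropriate follow-up period". The AE definition in Protocol 12.1.1.1 includes worsening, since it covers an unfavorable "symptom, syndrome, or illness that develops or worsens during the clinical study". The same section makes a pre-existing medical condition that has worsened an AE in its own right.

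Laboratory abnormalities follow a different rule. Under SAP 9.6 a graded abnormality after the start of study drug that "represents at least one-grade increase from the baseline assessment is defined as treatment emergent". Protocol 13.3.5 has the same rule.

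**The concern.** The primary objective is safety, and most of its endpoints depend on which AEs count as treatment-emergent. A date-only rule treats an AE that was open and mild at first dose, and became severe on drug, in the same way as one that was open and never changed: both are left out of the tables.

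The period before dosing is not empty. It includes screening and, for some subjects, androgen washout with an extra liver panel (Protocol 10.3.1). Protocol 5.7 names transaminase elevation as an important potential risk. An ALT rise that is open as an AE at first dose and climbs a grade on BCX7353 would count toward the laboratory endpoint but could be absent from the AE endpoints. The same definition feeds the DMC safety summaries (SAP 5.1) and the rates per 100 person-years (SAP 9.3.5).

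**Working it through.** The plan gives no figure to reproduce: there is no sample size calculation and no formal test. The check is a reading of the rules, followed by simple arithmetic on scale.

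**1. How long an AE can be open before first dose.** Protocol 10.3.1 and 10.3.2 allow 28 days from screening to baseline. With Medical Monitor permission this extends by 42 days: 28 + 42 = 70 days. Consent may be signed before the screening visit, so AE recording can begin earlier still.

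**2. What the rules do with each kind of event.**

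| Event | Relevant rule | In the TEAE tables? |
|---|---|---|
| Condition present before consent, worsens after first dose | Protocol 12.1.1.1 makes the worsening an AE | Yes, if dated at the worsening |
| AE starts between consent and first dose, does not worsen | SAP 9.3 exclusion | No, as intended |
| AE starts between consent and first dose, worsens on drug, new record dated at the worsening | SAP 9.3 definition | Yes |
| AE starts between consent and first dose, worsens on drug, original record kept | SAP 9.3 exclusion | No; listings only |

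Nothing in either document chooses between the last two rows. Protocol 12.1.2 says how long AEs are followed, but not whether a change of grade opens a new record.

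**3. Contrast with the laboratory rule.** Take ALT at DMID Grade 2 at baseline and Grade 3 on drug. The rise is one grade, so the laboratory endpoint counts it. If the same finding was recorded as an AE before first dose and the record is kept, the Grade 3 or 4 AE endpoint does not.

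**4. Scale per subject.** One reclassified subject moves a proportion by 100/N percentage points.

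- On the 227 treated at the interim (Protocol 5.2.2): 100/227 = 0.44 points.
- On the 475 planned (Protocol 8.1): 100/475 = 0.21 points.

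**5. Illustration on interim figures.** Protocol 5.2.2 reports 15.0% of subjects with a Grade 3 or 4 TEAE: 0.150 × 227 ≈ 34, and 34/227 = 15.0%. Adding 1, 3 or 5 subjects, which are assumed numbers:

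- 35/227 = 15.4%
- 37/227 = 16.3%
- 39/227 = 17.2%

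For discontinuation due to a TEAE, 19/227 = 8.4% becomes 20/227 = 8.8% with one more subject. These figures show sensitivity. They do not estimate how many events were missed.

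**The case against.** The strongest reply is that the protocol already captures worsening. An AE is something that develops or worsens, and a worsened pre-existing condition goes on the AE page with wording that shows the change. A record dated at the worsening then satisfies SAP 9.3, which speaks of AEs that occurred, not AEs that started. For laboratory findings, Protocol 12.1.1.1 limits AE reporting to changes from baseline, and SAP 6.6 sets baseline as the last value before first dose. On that reading a washout ALT rise is the reference, and a further clinically significant rise on drug is reportable with a post-dose date.

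Much of this stands. A reader might infer that every AE that begins before dosing and worsens on drug is dropped from every TEAE table. The documents do not support that, because the outcome depends on how the worsening is recorded. The reply still does not settle the case of an AE already open at first dose. An AE that spans first dose has also occurred before it, and the exclusion sentence then applies.

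Other points on that side:

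- **Liver safety is covered elsewhere.** SAP 9.6 has the Grade 3 or 4 laboratory endpoint, fold-ULN summaries, Kaplan-Meier plots and androgen subgroups. All AEs are listed, and reasons for discontinuation appear in disposition. This limits the harm but does not correct the AE endpoints.
- **No shortfall is visible at the interim.** Among the 40 subjects who had stopped androgens within 2 weeks of dosing, 25.0% had an ALT-increased TEAE and 32.5% had ALT > 3 × ULN. Other liver terms add 2.5%, 5.0% and 2.5%. Subjects may overlap across terms and grades differ, so the comparison neither shows nor excludes under-counting.
- **Versions differ.** The SAP lists protocol versions 1.0 to 5.0 and about 225 subjects; the current protocol says a detailed SAP will be developed. The 70-day extension comes from the current protocol, while direct rollover from a parent study belongs to the SAP design. The current protocol excludes investigational drug within 30 days before screening. The rollover route therefore concerns only the SAP cohort. The gap itself does not depend on it, since SAP 9.3 expects AEs before dosing.

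**Conclusion.** The point holds in conditional form. SAP 9.3 leaves out of the TEAE tables, by a stated rule, an AE open before first dose that worsens on BCX7353 **if** it is kept under its original record, and neither document says how that worsening is recorded. The effect can only lower the TEAE, serious TEAE, Grade 3 or 4 AE and discontinuation-due-to-TEAE proportions. Drug rash also rests on treatment-emergence, but a rash that began before any BCX7353 is unlikely to be judged drug-related.

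The size is 0.44 points per missed subject on 227 and 0.21 points on 475. The number of such subjects cannot be computed.

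A reader might be tempted to derive an expected count of missed liver events. That would need the share of subjects stopping androgens in screening, the share of those with a liver AE recorded before dosing, and the share worsening on drug; the documents give none of these. Nor does the interim figure of 2 of 15 subjects (13%) whose post-baseline ALT > 3 × ULN was not treatment-emergent supply one. By the laboratory rule those values had not risen a grade from baseline, and nothing says they were recorded as AEs.

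The remedy is small and the endpoints serve the primary objective, so the text should be changed.

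**What to change.** In SAP 9.3, define a TEAE as either of the following, through 30 days after last dose:

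- an AE with onset on or after first dose; or
- an AE with onset before first dose that increases in severity grade or becomes serious on or after first dose.

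Restrict the exclusion of pre-dose AEs to those that meet neither condition. Interruption or discontinuation of drug without worsening should not by itself make an AE treatment-emergent.

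In the eCRF instructions, state that such a worsening is entered as a new AE record dated at the worsening, so that the onset date and grade used in the tables refer to the same event. State also that each worsening is counted once, because SAP 9.3.1 and 9.3.5 report event counts as well as subjects. For the SAP rollover cohort, apply the same rule to AEs ongoing at entry.

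The cost is one added SAP clause and one completion note. TEAE counts may rise slightly, and figures under the new rule will not be strictly comparable with the interim summaries unless those are rerun.

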7.1.2. Effectiveness Endpoints

Effectiveness endpoints will include the following:

- Number and rate of HAE attacks
- Durability of response (attack rate trend over time)
- Number and proportion of days with angioedema symptoms
- Patient-reported outcomes (HAE disease-specific AE-QoL questionnaire scores and TSQM Global Satisfaction scores)
- Number of attacks requiring attack medication
- Discontinuations due to lack of efficacy (through Week 48 only)
- Severity of attacks

Additional related details of HAE attacks (eg, symptoms, anatomical location, hospitalizations, emergency room visits, attack severity, attack duration) and number of days lost from work and/or school due to attacks will be summarized.

All attacks recorded by the subjects will be reviewed and confirmed or rejected according to a set of pre-defined rules prior to inclusion in effectiveness analyses. These rules, which have been constructed in concert with HAE-treating physicians, are outlined in the Statistical Analysis Plan (SAP).

8. SELECTION AND WITHDRAWAL OF SUBJECTS

8.1. Number of Subjects

Approximately 475 subjects are planned to be enrolled globally in the study, with approximately 250 subjects planned to be enrolled in the US, which includes any adolescent subjects enrolled in the substudy.

8.2. Subject Selection

8.2.1. Inclusion Criteria

Subjects must meet all of the following inclusion criteria to be eligible for participation in this study:

1. Males and nonpregnant, nonlactating females ≥ 18 years of age (main study) or ≥ 12 to 17 years of age (substudy).
2. Subjects with a clinical diagnosis of HAE Type I or II who, in the opinion of the Investigator, are expected to benefit from an oral treatment for the prevention of angioedema attacks. A clinical diagnosis of HAE Type I or II is defined as:
 - A C1 esterase inhibitor (C1-INH) functional level below the assay lower limit of normal as assessed during the screening period by chromogenic assay OR
 - Laboratory documentation of historical C1-INH functional level below the assay lower limit of normal OR
 - Subjects who currently use plasma derived or recombinant C1-INH based therapies for acute attacks or prophylaxis may use one of the following to confirm their diagnosis:
 - SERPING-1 gene mutation known or likely to be associated with HAE Type I or II as assessed during the screening period OR
 - A confirmed family history of C1-INH deficiency
3. Subject weight ≥ 40 kg.
4. Access to one or more targeted medications for the treatment of acute HAE attacks. The following are acceptable: icatibant, plasma-derived C1-INH (any form), ecallantide, recombinant C1-INH.
5. Female subjects must meet at least 1 of the following requirements:

- a. Be a woman of childbearing potential (defined as a nonmenopausal adult or adolescent-female who has not had a hysterectomy, bilateral oophorectomy, or documented ovarian failure) who agrees to use at least an acceptable effective contraceptive method during the study and for a duration of 30 days after last dose of study drug. One or more of the following methods are acceptable:
- Surgical sterilization (ie, bilateral tubal occlusion or vasectomy of male partner)
 - Placement of an intrauterine device (IUD) or intrauterine system (IUS) (implanted any time prior to or during screening)
 - Implantable or injectable progesterone hormonal contraception initiated at least 7 days prior to the screening visit
 - Combined (estrogen- and progestogen-containing) oral, intravaginal, or transdermal or oral progesterone norethindrone-based hormonal contraception initiated at least 28 days prior to the screening visit
 - Male or female condom with or without spermicide
 - Use of an occlusive cap (diaphragm, or cervical/vault caps) with spermicide (foam/gel/film/cream/suppository)

Female subjects who report being postmenopausal for ≤ 2 years and have a follicle-stimulating hormone (FSH) ≤ 40 mIU/mL must agree to use at least an acceptable effective contraceptive method and (as proposed above) during study and for 30 days after the last dose of study drug.

Female subjects of childbearing potential who declare themselves as either sexually abstinent or exclusively having female sexual partners do not need to use an acceptable method of contraception. This declaration should be reviewed with the subject throughout the study to ensure continued accuracy. Abstinence in this study is defined as “true abstinence: when this is in line with the preferred and usual lifestyle of the subject.”

- b. Be a woman of nonchildbearing potential (defined as postmenopausal for > 2 years or having an FSH > 40 mIU/mL if postmenopausal ≤ 2 years or have had a hysterectomy, bilateral oophorectomy, or documented ovarian failure).
6. Able to provide written, informed consent. Subjects aged ≥ 12 to 17 years who are screened for the substudy must be able to read, understand, and be willing to sign an assent form in addition to a caregiver providing informed consent.
7. In the opinion of the Investigator, the subject is able to adequately comply with all required study procedures for the duration of the study. The subject must demonstrate adequate compliance with all study procedures required including diary recording of HAE attacks.

